1.4 Benefits

All participating units and their patients, regardless of randomization assignment, stand to benefit from the education regarding opportunities for hand hygiene and other infection prevention practices. This education may lead to an increase in compliance with these practices and potentially may limit the spread of microorganisms to susceptible patients leading to decreased infection.

For Aim 1b, there will be no direct benefit to the HCW participants involved. They will benefit indirectly by knowing that they are contributing to a topic that affects them. The proposed study could lead to changes in policy regarding hand hygiene expectations, monitoring and feedback.

1.5 Risk Benefit Ratio

The potential benefits of this study outweigh the minimal risks to participants.

2 Study Objectives, Aims and Hypothesis

Aim 1A: Perform a multicenter, cluster randomized trial to evaluate the efficacy of a direct gloving strategy to improve compliance with infection prevention practices (i.e. HH and glove use).

Hypothesis: When compared to the standard practice of performing HH and then donning gloves, directly gloving when gloves are indicated will increase compliance with HH and glove use.

Aim 1B: Perform a nested multicenter validation study, where gloved hands of HCWs will be randomly sampled to determine bacterial contamination of non-sterile gloves after donning.

Hypothesis: When compared to the standard practice directly gloving when gloves are indicated will have no effect on bacterial contamination of gloves.

3 Study Design and Procedure

Aim 1A:

Study Design: We will perform a cluster-randomized trial to include 14 patient care areas (i.e. units) at the University of Maryland Medical Center (UMMC), the R Adams Cowley Shock Trauma Center (STC), University of Iowa Hospitals (UIH), and Johns Hopkins Hospital (JHH). Each unit will be randomly assigned to the intervention or usual care group. Randomization will be stratified by unit type: adult intensive care, general pediatric wards, emergency departments and inpatient hemodialysis units. One unit from each of the four types at UMMC, UIH, and JHH will be selected for study participation and will be randomized; and two units (one Adult ICU and the Trauma Resuscitation Unit (comparable to the Adult ED)) will be selected and randomized from Shock Trauma. We have specifically chosen these diverse areas to avoid any potential crossover of effect from one study unit to another as units have very different personnel with very little crossover of care.

In order to account for differences in baseline compliance with infection control practices including HH and glove use, baseline rates of compliance will be observed across all available units (this includes 4 adult ICUs, 3 general pediatric wards units, 1 ED and 1 inpatient HD unit at UMMC and 4 adult ICUs and 1 ED at Shock Trauma). In the study period prior to randomization; the final units will be selected based on similar baseline compliance. For example, there are 11 general pediatric wards across three sites. Baseline data will be collected and compared across all 11 wards. One pediatric unit from each facility with the closest baseline composite HH and glove compliance rates will be selected. Thus we are matching 3 general pediatric wards (one from each site) based on pre-intervention outcomes of interest to improve power and minimize the impact of measured and unmeasured confounders. Once selected, the units will be randomized to the intervention or usual care group. This process will be done for each unit type (e.g. adult ICU).

The study will begin with a 6-month period of baseline data collection in which HH and infection prevention compliance will be recorded in all units that are potentially available for inclusion as described above. During that time period the investigative team will develop and refine educational, training and data collection tools. Following this baseline period, a short “wash-in” period of 3 months will be used to educate and train HCWs in the participating units regarding expected infection prevention practices of HH and glove use. The intervention period will be a full 12 months. This will allow the intervention to be tested over a full calendar year accounting for differences in seasonality as well as different levels of training across an academic year.

All participating units regardless of intervention status will receive education regarding policies and procedures for compliance with infection prevention strategies including HH and glove/gown use. This education will be identical in both groups (intervention and usual care) and will be consistent with published guidelines (WHO/CDC) with the exception of HH prior to donning non-sterile gloves - which according to existing guidelines is an uncertain area where research is needed. HCWs from units randomized to the usual care group will receive education that states that they should perform HH prior to donning non-sterile gloves. HCWs from units randomized to the

intervention group will receive education that states that HH is not necessary prior to unsterile glove use. Both units will receive education around other necessary moments for HH and as stated this education will be identical for both groups.

Data collection in both the baseline and intervention phases will be as follows:

Primary Outcome:

Composite Compliance with expected infection prevention practices upon entry to Contact Precaution-patient rooms. HCWs in the usual care group will be recorded as compliant if HH AND glove use is observed at room entry; HCWs in the intervention group only need to have glove use observed to be considered compliant.

Secondary Outcomes:

1. Compliance with glove use upon entry to Contact Precaution-patient rooms for both groups
2. Compliance with HH upon entry to ALL patient rooms
3. Compliance with HH upon exit to ALL patient rooms

Additional Information collected will include: date, time and location (i.e. hospital/unit) of observation and the role of the HCW observed (e.g. MD, RN, other).

Note that all data collected is completely anonymous and no HCW identifying information will be collected nor reported

Aim 1B:

We will perform a nested, multicenter validation study in which we will randomly sample the gloved hands of HCWs entering Contact Precaution-patient rooms in both the intervention and usual care units. Sampling will occur at random and HCWs will not be told in advance that sampling will be performed. A research team member will approach potential participants immediately after gloves are donned and just prior to entering a Contact Precaution-patient room. HCWs will be asked if they have participated in this study previously and those that answer yes will be excluded from participation. Gloved hands of willing HCWs will be sampled via direct imprint of the non-dominant gloved hand onto an agar plate. In addition to sampling of gloved hand, additional data will be collected regarding the date, time and location of the observation, whether the unit was allocated to intervention or usual care, whether the HCW performed HH prior to donning non-sterile gloves, the HCW role (e.g. RN, MD, etc...), when the HCW had started their shift and the time since last performing HH. Each sample will be given a unique number, however, there will be no link to HCW participants and no identifying information will be collected. After sampling, agar plates will be assessed for microbial content including total colony counts and identification of specific pathogenic bacteria including *Staphylococcus aureus*, *Enterococcus*, *Enterobacteriaceae*, *Pseudomonas aeruginosa* and *Acinetobacter baumannii*.

4 Selection and Withdrawal of Participants

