6.2 Sample Size Estimates

Aim 1A:

How many participants (or specimens, or charts) will be used in this study?

UMMC: 6 units Worldwide: 14 units

14 units will be randomized to intervention or usual care. Over the 12-month study period we expect a minimum of 7000 total observations (14 units across the systems x 500 observations). Each system will have a research coordinator perform observations 3 hours per day four days per week. We estimate an average of 5 observations per hour¹⁹ (15 per day and 60 per week) and thus over 2500 observations per year per research coordinator are feasible (we expect to require fewer to achieve desired power). Average HH compliance is consistently at 40-50% and are often lower when glove use is indicated^{1,15}, we believe the compliance with infection prevention practices (i.e. primary outcome, composite compliance with HH AND glove use) in the usual care group will be ~40%. Recent studies have shown compliance with gloves when indicated to be approximately 70-80%¹⁵. Thus for the primary outcome, we expect a difference in compliance with infection prevention practice to be ~ 30%. If we assume 500 observations per area, an alpha level of 0.05, an interclass coefficient of 0.001²² we will require inclusion of 4 patient care areas (2 experimental and

2 usual care) to achieve a power greater than 90% power to detect an effect size of 30% (i.e. the primary outcome). If we vary the interclass coefficient to 0.01, we still have greater than 90% power under the same conditions. Relative to the secondary outcome, in which we will compare compliance with gloving only in both the direct gloving (i.e. experimental group) and the usual care group, we believe it is reasonable to expect that removing the cumbersome and time-consuming requirement of HH prior to glove use may increase compliance with glove use when indicated by approximately 10%. Using the same assumptions as the primary aim with an interclass coefficient of 0.001, we need to recruit and randomize 4 participating units to achieve > 90% power to detect this effect size of 10%. If we use the higher interclass coefficient of 0.01, we need 8 participating units to achieve > 85% power. So in short, we have ample power to see an effect in both primary and secondary outcomes including the sub-populations of adult ICU, dialysis and emergency department.

Aim 1B:

How many participants (or specimens, or charts) will be used in this study?

Local: 866 Worldwide: 2600

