Based on pilot data, we anticipate 5% of HCWs in the usual care group (hand-hygiene plus gloves) and 3.5% in the experimental group (direct gloving) to have > 30 CFUs. We define non-inferiority as a relative risk < 1.15 of having > 30 CFUs, comparing the experimental group to the usual care group. That is, delta equal to 1.15. Under these assumptions, 1280 samples (per group) are sufficient for a one-sided test with alpha=0.025 to have 80% power to detect noninferiority.²³ 1280 samples in both groups will result in a total of 2560 samples for the 12-month study period. Spread across the 14 proposed participating units at the 3 healthcare systems (UMMC and STC will share a Research Associate), this is approximately 850 samples per site and 180 samples per participating unit over the 12-month study period. Thus, each site will need to recruit just over 70 HCWs each month to meet the goal sample size. In the pilot study 230 HCWs were recruited and agreed to participate in a single month.

7 Data Collection, Handling and Storage

All data collected will be stored in a relational database in order to digitize the data for analysis. No PHI will be collected. The database will be stored on a shared drive. Data from University of Iowa and Johns Hopkins Hospital will be sent electronically the investigators at the University of Maryland – data from Aim 1A is aggregate unit level data and not-human subjects data; and data from Aim 1B is completely de-identified.

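### Randomisation stratified by unit type alone does not guarantee 7:7 arms, 1280 glove samples per group, or both arms within every hospital system

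*Combined protocol and SAP*

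**What the plan says.** Section 3 (Study Design and Procedure, Aim 1A) gives the only randomisation rule: "Randomization will be stratified by unit type: adult intensive care, general pediatric wards, emergency departments and inpatient hemodialysis units". On which units enter, it says "One unit from each of the four types at UMMC, UIH, and JHH will be selected for study participation and will be randomized", and adds that "two units (one Adult ICU and the Trauma Resuscitation Unit (comparable to the Adult ED)) will be selected and randomized from Shock Trauma". Section 6.2 confirms the count for the Maryland system: "UMMC: 6 units Worldwide: 14 units".

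For Aim 1B, Section 6.2 states "1280 samples in both groups will result in a total of 2560 samples for the 12-month study period", and translates this into "approximately 850 samples per site and 180 samples per participating unit over the 12-month study period". It counts three healthcare systems, with UMMC and Shock Trauma sharing a research associate, and expects each site to recruit just over 70 workers a month.

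Section 6.1 uses robust standard errors for within-site clustering in Aim 1B. The covariates it names for Aim 1A are examples, baseline hand hygiene compliance and frequency of Contact Precautions. Site is not named for either aim. The documents give no allocation ratio within a stratum, no 7:7 rule, no balance by site and no sample quota per arm.

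**The concern.** Two of the four strata hold three units and cannot split evenly. If both lean the same way, the trial is 8:6. Because site plays no part in the randomisation, all units of one system can also land in the same arm.

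The second possibility matters more. A system wholly in one arm offers no within-system comparison, so its local practice, its patients and its laboratory or field procedures are inseparable from treatment there. Section 6.2 gives each system its own research coordinator to make the observations. Observer and arm would then coincide too, for a primary outcome recorded by direct observation. With 14 clusters, little is available to average this out.

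The Aim 1B targets add an ambiguity. Equal numbers per site and equal numbers per unit are different recruitment plans when systems hold 6, 4 and 4 units, and they give different arm totals for the same allocation.

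**Working it through.** **Inputs.** Section 3: UMMC, Iowa and Hopkins have one unit of each type, and Shock Trauma adds an adult ICU and the Trauma Resuscitation Unit. The strata are therefore adult ICU 4 (Maryland 2, Iowa 1, Hopkins 1), ED/TRU the same, pediatrics 3 (one per system) and hemodialysis 3 (one per system). Section 6.2: 5% versus 3.5% with more than 30 CFUs, relative-risk margin 1.15, one-sided alpha 0.025, 80% power, 1280 per group, total 2560.

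**The plan's figure.** On the difference scale the margin is 0.15 × 0.05 = 0.0075, and the distance from the expected difference is 0.015 + 0.0075 = 0.0225. Then n = (1.960 + 0.842)² × (0.05 × 0.95 + 0.035 × 0.965) / 0.0225² ≈ 1261 per group, within 1.5% of 1280. Power at 1280:1280 is 80.6%. This scale is used below because it reproduces the plan.

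**Assumption.** Splits are as even as possible within type: 2:2 in the 4-unit strata, 2:1 or 1:2 in the 3-unit strata, all equally likely. Each stratum has 6 possibilities, so there are 6⁴ = 1,296 allocations.

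**Arm sizes in units.** The split is 7:7 only when pediatrics and hemodialysis lean opposite ways, so P(7:7) = 1/2. Otherwise it is 8:6 or 6:8.

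**A whole system in one arm.**
- Iowa: 2 × (1/2)⁴ = 12.5% (162 allocations). Hopkins is the same.
- Maryland: 2 × (1/6 × 1/6 × 1/2 × 1/2) = 1.4% (18 allocations).
- At least one, after removing overlaps: 162 + 162 + 18 − 34 − 8 − 8 + 2 = 294, and 294/1,296 = 22.7%.

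As a sensitivity check, suppose each unit were assigned by an independent coin toss. At least one system would be wholly in one arm with probability 1 − (7/8)² × (31/32) = 25.8%, and P(7:7) would fall to 20.9%. The risk to systems hardly depends on the assumed ratio.

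**Sample targets.**

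| Reading | Maryland (6 units) | Iowa (4) | Hopkins (4) |
|---|---|---|---|
| Equal per system, 2560/3 ≈ 853 | 853/6 ≈ 142 per unit | 853/4 ≈ 213 per unit | 213 per unit |
| Equal per unit, 2560/14 ≈ 183 | 1097 in total | 731 in total | 731 in total |

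**Resulting Aim 1B groups.** With equal unit targets, 1280:1280 arises in 50% of allocations; the rest give 1463:1097 one way or the other. With equal system targets, 1280:1280 arises in 252/1,296 = 19.4%. The smaller arm then has a median of 1138 and a minimum of 853.

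**Power.** For 8:6 or 6:8 with equal unit targets: 78.9% to 80.8%, depending on which arm is larger. Averaged over all allocations with equal system targets: 80.0%. Worst case: 73.6%, in one allocation (1/1,296 ≈ 0.08%).

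**Constrained set.** Requiring 3:3 in Maryland, 2:2 in Iowa and 2:2 in Hopkins leaves 108 of the 1,296 (8.3%). All 108 are 7:7, with pediatrics and hemodialysis split in opposite directions. Each unit is in the intervention arm in 54 of 108, that is 50%. With equal system targets each arm gets 853.3 × (1/2 + 1/2 + 1/2) = 1280, and with equal unit targets 7 × 182.86 = 1280. Both Shock Trauma units share an arm in 48/108 = 44%, against 50% without the constraint.

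**The case against.** Stratifying by unit type is a recognised choice and the randomisation remains valid: about 77% of allocations leave no system wholly in one arm. Section 3 matches units across sites on baseline compliance before randomisation, and Section 6.1 adjusts Aim 1A for baseline hand hygiene compliance. For the primary outcome, Section 6.2 claims more than 90% power with only 4 units, so on the plan's own figures an 8:6 split of 14 is immaterial. The Aim 1B figures of 850 and 180 are both approximate averages of one total, and neither is stated as a fixed quota.

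Most of this stands, and it rules out some stronger readings. A reader might infer that the design will miss 1280 per group. The documents do not support that: some allocations reach it exactly, and nothing stops the team from setting unit targets by arm once units are assigned. A reader might also infer a material loss of power, but the average loss is about half a percentage point. Nor are 850 and 180 arithmetic errors.

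The system-level confounding remains. The matching uses compliance, not glove contamination, which is the Aim 1B outcome. UMMC lists only one ED and one hemodialysis unit, so it has no choice of unit to match in those two types. Adjustment for baseline compliance does not cover Aim 1B and does not separate observer from arm. The quota ambiguity also remains, because a stated monthly figure for each site implies equal site recruitment, which does not give 180 in every unit.

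**Conclusion.** The point holds as an avoidable design weakness, not as an error that invalidates the trial. The stated scheme does not guarantee 7:7 arms (missed in 50% of allocations), 1280 samples per group (reached exactly in 19% under equal system targets and 50% under equal unit targets), or both arms in every system (at least one system wholly in one arm in about 23%). These figures assume splits as even as possible within type, all equally likely, and count UMMC and Shock Trauma as one system, as Section 6.2 does for Aim 1B. The power figures further assume the difference scale and no clustering.

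Power alone would not justify a change. The case rests on the risk that system, and its observer, coincide with treatment in a trial whose own Aim 1B analysis expects sites to differ.

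**What to change.** After units are selected and before any is assigned, draw one allocation at random from the 108 that meet all of these conditions: 2:2 in adult ICU; 2:2 in ED/TRU; opposite 2:1 and 1:2 splits in pediatrics and hemodialysis; and 3:3, 2:2 and 2:2 in the Maryland, Iowa and Hopkins systems. State in Section 3 that balance is by system and not by the four hospitals, since both Shock Trauma units can still fall in one arm.

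In Section 6.2, choose one Aim 1B target and state what it implies: about 853 per system, hence about 142 per Maryland unit and 213 per Iowa or Hopkins unit; or about 183 per unit, hence about 1097, 731 and 731 per system. Either gives 1280 per arm under the constrained draw.

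The cost is one protocol sentence, a short allocation list and one corrected line of targets. The drawback is fewer possible allocations, 108 instead of 1,296. That is still enough for a permutation test: the set is symmetric under swapping arms, so the smallest two-sided p-value is 2/108 ≈ 0.02.

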6.1 Analysis Plan

Aim 1A:

We will assess whether primary and secondary outcomes are significantly different in the experimental and usual care groups using the generalized estimating equations (GEE) approach with an unstructured working correlation matrix to adjust for clustering. We will perform multivariate analyses using GEE adjusting for covariates such as baseline compliance with HH and frequency of Contact Precautions. Analyses will be conducted at the level of the participating unit and will follow the intention to treat approach.

Aim 1B:

The primary analysis will be an intention-to-treat analysis where the gloved hands of HCWs sampled in the usual care group will be compared to those in the Intervention group regardless of HH activity. A secondary, as-treated analysis will be performed where HCWs who were observed to perform HH and then don gloves will be compared to those in which gloves were directly applied without performing HH. The primary, intention-to-treat analysis will provide great insight into the effectiveness of this intervention while the secondary, as-treated analysis will validate efficacy.

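### The Aim 1A primary outcome uses an easier compliance rule in the intervention arm, and on the plan's figures that scoring gap alone equals the whole planned 30-point effect

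*Combined protocol and SAP*

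**What the plan says.** Section 3 (Aim 1A) defines the primary outcome as "Composite Compliance with expected infection prevention practices upon entry to Contact Precaution-patient rooms". In usual care, both HH and gloves must be observed at entry. In the other arm, "HCWs in the intervention group only need to have glove use observed to be considered compliant". The first secondary outcome applies one rule to everyone: "Compliance with glove use upon entry to Contact Precaution-patient rooms for both groups". HH at entry to and exit from all rooms is also secondary.

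Section 6.2 sets the planning values. On the "primary outcome, composite compliance with HH AND glove use) in the usual care group will be ~40" per cent. On gloves: "Recent studies have shown compliance with gloves when indicated to be approximately 70-80" per cent. From these two figures it infers a primary difference of about 30 points. A gain in glove use of about 10 points is stated separately, under the secondary outcome.

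Section 2 states the Aim 1A hypothesis as an increase in compliance with HH and glove use, and the Summary speaks of both. Two features deal with baseline differences. Units are chosen by matching (for example, "One pediatric unit from each facility with the closest baseline composite HH and glove compliance rates will be selected"), and the GEE models in section 6.1 will be run "adjusting for covariates such as baseline compliance with HH and frequency of Contact Precautions".

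**The concern.** The same observed event, gloves on without HH, is scored differently according to the arm in which it occurs. The primary contrast therefore adds two things together: any real change in behaviour, and the share of entries made with gloves but without HH. The second part is created by the definition and always favours the intervention, because within one population HH plus gloves cannot be more frequent than gloves.

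If that part is as large as the planned effect, the primary test is almost certain to be positive whether or not direct gloving changes what staff do. It could be strongly positive while glove use is unchanged or worse. The protocol does not say which result governs the conclusion if the primary and secondary outcome 1 disagree. Section 1.2 expects the Aim 1A results to support guideline change, so the difference matters.

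**Working it through.** **Inputs.** From section 6.2: usual-care composite 40%; glove use 70-80%; planned difference 30 points; expected glove gain 10 points; 500 observations per unit; alpha 0.05; ICC 0.001 and 0.01; 14 units. Assumed here: two-sided test; 7 v 7 allocation; all 500 observations are Contact Precautions entries, as the plan's own power statement for this outcome implies; ICCs of 0.02 and 0.05 as sensitivity values.

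**Formulas.** Design effect DE = 1 + 499 × ICC. Effective n per arm = units per arm × 500 / DE. SE = √{[p₁(1−p₁) + p₂(1−p₂)] / n}. z = |p₁ − p₂| / SE. Power is from the noncentral t with 12 df for 14 units, unless stated otherwise.

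**Step 1: the plan's own figures.** With 2 v 2 units and 40% v 70%, the effective n per arm is 1000/1.499 = 667 at ICC 0.001 and 1000/5.99 = 167 at ICC 0.01. Normal-approximation power exceeds 99.9% in both cases, so the stated figure of more than 90% reproduces. (A t test on 2 df gives 99.9% and 81%.) For gloves, 70% v 80%, the same approximation gives 98.8% with 4 units at ICC 0.001 and 84.9% with 8 units at ICC 0.01. The plan states more than 90% and more than 85%. The power arithmetic is not the problem.

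**Step 2: the scoring gap with identical behaviour.** Expected difference = glove rate − composite rate. This is 70 − 40 = 30 points, 75 − 40 = 35, or 80 − 40 = 40. None of the 10-point glove gain is needed to reach 30. If gloves did rise from 70% to 80%, the primary would show 40 points: 30 from scoring and 10 from behaviour.

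**Step 3: the primary test when nobody changes behaviour** (40% composite and 70% gloves in both arms, 7 v 7). At ICC 0.01, n = 3500/5.99 = 584, SE = √[(0.24 + 0.21)/584] = 0.0278 and z = 0.30/0.0278 = 10.8.

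| ICC | z | Runs favouring intervention |
|---|---|---|
| 0.001 | 21.6 | 100% |
| 0.01 | 10.8 | 100% |
| 0.02 (assumed) | 8.0 | 100% |
| 0.05 (assumed) | 5.2 | 99.6% |

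The last column is from 20,000 simulated trials with unit-level t tests standing in for GEE. Usual-care entries were split 40% HH plus gloves, 30% gloves only and 30% no gloves. In the same runs at ICC 0.01, the same-rule glove test rejects in 5.4%, close to its nominal level.

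**Step 4: glove use falls in the intervention arm** (70% to 60%, an illustrative scenario). The primary still shows 60 − 40 = +20 points, with z = 0.20/0.0287 = 7.0 at ICC 0.01.

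| ICC | Primary favours intervention | Gloves significantly worse | Both |
|---|---|---|---|
| 0.01 | 100% | 90.8% | 90.8% |
| 0.02 (assumed) | 99.6% | 68.6% | 68.2% |
| 0.05 (assumed) | 85.8% | 35.7% | 25.6% |

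At ICC 0.01 the primary keeps 90% power until intervention glove use is about 50.2%, and 80% power until about 48.8%.

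**Step 5: sensitivity to the inputs** (no behaviour change, gloves 70%, ICC 0.01). With an assumed composite of 50%, z = 7.1 and rejection is about 100%. With 60%, z = 3.6 and rejection is 91%. Splitting the units 6 v 8 gives z of 10.65-10.75 for Step 3 and 90.3% for the joint result in Step 4.

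**Step 6: do matching and adjustment help?** Both act on baseline differences between units. Neither changes how an entry after randomization is scored, so the gap in Step 2 remains.

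**The case against.** The strongest reply is that this is a declared choice. The policy is what is randomized, the outcome is compliance with the practice expected in each arm, and the rule is stated openly. Read that way, the composite is a legitimate measure of adherence to assigned policy, and the hypothesis could be read in the same sense. The first part stands. The second does not rescue the primary: permission to omit HH is not evidence of more HH, and the Summary presents the gain as one that protects patients.

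The same-rule glove outcome and HH at entry and exit are already secondary outcomes in the same GEE plan, and section 1.3 commits to monitoring HH. That is correct and makes the remedy cheap. It does not settle which result governs.

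The 40% and the 70-80% come from different sources, and the plan does not say outright that the glove figure was seen under an HH-first policy. With a composite of 50% the gap would be 20-30 points. The exact size is therefore uncertain, but the direction is not. The plan also gives no reason to expect glove use to fall; Step 4 shows what the primary would fail to detect and is not a forecast.

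Finally, section 6.2 does not say that all 500 observations are Contact Precautions entries. If fewer are, the primary is still near-certain to reject (z = 6.9 for 40% v 70% with an assumed 50 per unit at ICC 0.01). Power for the glove outcome does suffer, as set out under the fix.

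**Conclusion.** The concern holds and must be fixed. On the plan's own figures the difference in scoring rules is worth 30-40 points, which accounts for the entire planned effect of about 30 with no change in behaviour. A positive primary result is then almost guaranteed at the plan's ICCs and remains so at an assumed 0.05. It would show adherence to an easier assigned policy and could not by itself support the Aim 1A hypothesis. The rejection rates assume 7 v 7 units, 500 Contact Precautions entries per unit and unit-level t tests in place of GEE. The direction of the gap needs none of these assumptions. Confidence is high.

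**What to change.** Make secondary outcome 1, glove use at entry to Contact Precautions rooms scored alike in both arms, the primary outcome. At minimum, state that any claim of improved compliance rests on it. Requiring both it and the composite as co-primary would also work. At the planning values the composite is positive in about 100% of trials, so the glove test would decide.

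Keep the arm-specific composite, label it as adherence to assigned policy, and show its HH and glove components by arm. Align the Aim 1A hypothesis with the chosen primary. Make the 10-point glove effect the governing calculation in section 6.2, restated for 14 units.

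A minor addition: the entry HH outcome, "Compliance with HH upon entry to ALL patient rooms", should be reported separately for Contact Precautions and other rooms, so that the taught omission of HH is not mixed with spillover. Room type is already needed to score the outcomes and should be added to the listed data fields.

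**Cost.** No new observations or units are needed. Power with 7 v 7 units and 500 entries each:

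| Glove use | ICC 0.01 | ICC 0.02 (assumed) | ICC 0.05 (assumed) |
|---|---|---|---|
| 70 to 80% | 95% | 77% | 42% |
| 75 to 85% | 98% | 83% | 48% |
| 80 to 90% | 99% | 91% | 57% |

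There are two real downsides. Power depends far more on the ICC, and on the number of Contact Precautions entries, than it does for a 30-point effect. For 70 to 80% at ICC 0.01 it is 92%, 81% or 64% with an assumed 250, 100 or 50 entries per unit. Glove use alone also leaves the HH half of the hypothesis to the secondary outcomes.
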